### **23.1.2 Primary Objective**

The primary objective of the TRTT is to assess the efficacy of TRT, defined as DC and ST achieved through conventional SGs (Group 1) as a treatment for severe debilitating tinnitus. The primary outcome to be measured in the TRTT is the difference in scores on the Tinnitus Questionnaire (TQ) between baseline and follow-up assessed longitudinally, at 3, 6, 12, and 18 months of treatment. The corresponding hypothesis is that TRT (Group 1 in Table 22.1) compared with the standard of care (SC; Group 3) will reduce the severity of debilitating tinnitus significantly as assessed by longitudinal changes in the TQ score and at the end of treatment..

The secondary efficacy outcomes will test the following hypotheses. TRT (Group 1) compared with SC (Group 3) will reduce severity of debilitating tinnitus significantly as assessed by longitudinal changes in:

Score on the following tinnitus and functional measures:

- Sub-scales of the TQ;
- Tinnitus Handicap Inventory;
- Tinnitus Functional Index;
- TRT Visual Analogue Scale; and
- Digit Symbol Substitution Task.

and psychoacoustic measures:

- Tinnitus Pitch and Loudness Match; and
- Loudness Discomfort Level (LDL)

### **23.1.3 Secondary Objectives**

The secondary objectives are to investigate the efficacy of each of the TRT components, DC and ST achieved with conventional SGs. Specifically, we will:

1. Investigate whether ST using conventional SGs is more effective in treating Study Participants with debilitating tinnitus compared with placebo SGs given that both groups are assigned to DC (Group 1 versus Group 2).
2. Investigate whether DC is more effective in treating Study Participants with debilitating tinnitus compared with usual care (Group 2 versus Group 3). We assume that the effect of placebo ST is negligible.

The primary and secondary efficacy outcomes and hypotheses are similar to those for the primary objectives. Specifically, we hypothesize that the reduction in severity of tinnitus will be higher in Study Participants assigned to (1) Group 1 (DC + conventional SG) compared with those assigned to Group 2 (DC + placebo SG); and also in (2) Group 2 (DC + placebo SG)

compared with those assigned to Group 3 (SC) as assessed by longitudinal changes in the TQ score. Secondary efficacy outcomes are change, assessed longitudinally and also at the end of treatment in the following:

Score on the following tinnitus and functional measures

- Sub-scales of the TQ;
- Tinnitus Handicap Inventory;
- Tinnitus Functional Index;
- TRT Visual Analogue Scale; and
- Digit Symbol Substitution Task.

and psychoacoustic measures:

- Tinnitus Pitch and Loudness Match; and
- Loudness Discomfort Level (LDL)

## 23.2 Sample Size Considerations

The overall objectives of this study are thus three-fold, i.e. to assess the:

- Efficacy of TRT (DC + conventional SG) compared with SC;
- Superiority of conventional SG over the placebo SG given the patients in comparison groups are exposed to DC; and
- Superiority of DC over SC, given the assumption that there is no or little effect of placebo SG.

The primary outcome measure is change in the TQ score. Thus, the TRTT is designed primarily to have sufficient power to detect the minimal clinically important difference between these study groups as designated by clinical experts. This approach allows us to detect important differences, yet not waste resources on power to detect unimportant differences.

### 23.2.1 Determination of the Minimal Clinically Important Difference

Consultation with experts familiar with the TQ were used to estimate the change in the TQ that would be deemed clinically important. [name] (the developer of the TQ instrument) proposed that “An effect size of 0.8 or perhaps 1.0 on the Emotional Distress subscale is a reasonable criterion for [clinically] significant change.” An effect size of 0.8 to 1.0 on the full TQ would correspond to a change of approximately 10 to 13 points. [name], a researcher with extensive experience using the TQ stated “I personally believe that a change of less than 5 to 6 points does not mean much.” Based on this input, the TRTT has been designed to have good power to detect a 10-point difference for the primary objective (i.e., between Group 1 and Group 3) and a 7-point difference for the secondary objectives (i.e., between Group 1 and Group 2 or between Group 2 and Group 3) with respect to the longitudinally assessed change in TQ.

A review of the literature suggests that an effect of this size is plausible. A brief review of four studies that assessed the effectiveness of the TRT or TRT-like intervention as measured by the TQ is shown in Table 23.2.

**Table 23.2. Changes in TQ Score after TRT or TRT-like Interventions**

Study	Sample Size	Length of follow-up (weeks)	Mean TQ at baseline	Mean TQ at follow-up	Change
Goebel, Rubler, Stepputat et al. (1999)	10	16	47.2	39.7	-7.5
Biesinger, and Greimel (1999) 	42	52	56.4	42.3	-14.2
Haerkotter (2001)	28	26	53.7	29.5	-24.2
Delb, D'Amelio, Boosten, and Plinket (2002)	27	26	46.5	32.1	-14.4
Zachriat (2003)	30	52	44.5	29.1	-15.4

 Exact numbers were abstracted from Table 4 in Goebel and [name] (1999).

TRT or TRT-like interventions are shown in Table 23.2 to achieve substantial changes in these earlier studies, although the sample size in each study is quite small.

To estimate expected changes in TQ in the “usual” care groups, a literature survey was completed. Four studies were found using wait list controls and are summarized in Table 23.3.

**Table 23.3. Changes in TQ Score for Wait List Controls**

Study	Sample Size	Length of follow-up (weeks)	Mean TQ at baseline	Mean TQ at follow-up	Change
Goebel and [name], 1995	138	26 to 52	52.0	51.2	-0.8
Kroner-Herwig and Esser, 1999	20	30	38.7	35.9	-2.8
Goebel, Rubler, Stepputat et al. , 1999	27	26	56.1	57.1	1.0
Delb, D'Amelio, Boosten, and Plinket (2002)	27	12	48.1	47.4	-0.7

Three studies examined the effect of “education” or other types of “counseling”. These are shown in Table 23.4.

**Table 23.4. Changes in TQ Score for Counseling Controls**

Study	Sample Size	Length of follow-up (weeks)	Mean TQ at baseline	Mean TQ at follow-up	Change
Kroner-Herwig et al. , 1997 	16	8	36.3	28	-8.3
Von Wedel et al. , 2000	49	12	47.2	42.8	-4.4
Schmidt and Kroner-Herwig, 2002	23	4	43	38	-5

 Exact numbers were abstracted from Table 4 in Goebel and [name] (1999).

On average, there is only about a 5-point change with various types of counseling, although the studies had small sample sizes and short follow-up times.

### 23.2.2 Variation in Changes in TQ after Treatment.

We also surveyed the literature and contacted TQ experts to obtain information on variances in the changes to be expected in order to calculate power. Results are summarized in Table 23.5.

### 23.2.3 Sample Size Calculations

For the sample size calculations, we have made the following assumptions:

- Type-I error rate = 0.05
- Two sided test;
- 10-point clinically significant difference in mean TQ scores for primary comparison (DC + conventional SG versus SC);
- 7-point difference for hypothesized partial comparisons: SG (DC + conventional SG versus DC + placebo SG) and DC (DC + placebo SG versus SC);
- Power of 80% of comparisons of partial interventions to drive the sample size calculations;
- Equal standard deviation of 12.5;
- Four follow-up treatment time points (3, 6, 12, and 18 months); and
- 10 % attrition rate

We used Power and Sample Size Calculations (Dupont and Plummer) to calculate an estimated sample size for the TRTT. We divided  $\alpha$  of 0.05 among the three major comparisons. Using this software, we estimate that a total of 228 Study Participants or 76 Study Participants in each of the 3 groups will be required to yield at least 80% power to detect a 7-point difference for analyses of the TRT components, ST and DC. This sample size will provide for greater than 95% power for the primary analysis (comparison of TRT (Group 1) to the standard of care (Group 3)), taking into account a 10 % drop-out rate. The sample size estimation is a conservative estimate as the primary outcome is a longitudinal analysis using data from follow-up visits at 3, 6, 12 and 18 months.

Table 23.6 illustrates the sample size sensitivities to changes in the expected differences in TQ scores using these assumptions and standard deviation of 12.5.

**Table 23.6. Sample Size Sensitivities**

Difference in TQ score	Power		
	80%	90%	95%
10	113	147	173
8	173	223	270
7	228	290	350
6	307	397	477

With these assumptions, we estimate that with 228 Study Participants (to allow for 10% attrition), we will have greater than 95% power to detect a difference of 10 points in the TQ score of Study Participants assigned to TRT compared with SC, either as a longitudinal analyses or if measured at a single time point at the end of 18 months of treatment . We will have 80% power to detect a 7-point difference in the TRT components i.e, efficacy of sound therapy by comparing conventional SG with placebo SG for individuals assigned to DC; and efficacy of DC by comparing individuals assigned to DC + placebo SG with SC. These sample sizes will also have sufficient power to account for an equivalent point change in the “Emotional Distress” sub-scale.

### 23.3 Data Analysis

Analyses will be performed based on the principle of intention to treat, i.e., in the analysis Study Participants will be included in the group to which they were randomized, regardless of whether they adhered to the treatment. For the primary outcome, the only participants that will

not be included will be those for whom TQ could not be assessed at any follow-up visit due to loss to follow-up. However, we anticipate that few, if any, participants will not be able to complete at least one follow-up TQ measure. In addition, we have allowed for completion of the TQ by mail. Any report of our results will include an accounting of the numbers lost to follow-up and the reasons for the loss.

### **23.3.1 Interim Data Reports**

At least twice each year, the data files at the Coordinating Center will be "frozen", i.e., a copy or "snapshot" is made of the files as they exist on a specified date, in preparation for generating reports for the Data and Safety Monitoring Board (DSMB). Every effort will be made to insure that all error corrections and updates have been applied to the analysis sample. The data for interim analysis will be extracted from the database into flat files and converted into SAS or STATA data set format. In these formats, the data may be transformed, new analysis variables computed, and subjected to a variety of statistical analyses using procedures built into these analytic programs.

The main objective of each report is to present the accumulated data with sufficient detail and clarity through appropriate statistical analysis to permit evaluation of treatment benefit or harm. These reports include information regarding progress of the study, data quality, and comparisons of participants assigned to different management strategies within the randomized trial for the outcomes of interest. The specific contents of each report are developed by the Coordinating Center statisticians in collaboration with the DSMB. The interim reports are provided only to the DSMB and not to the Study Chair's office or collaborating Clinical Centers.

The same steps will be performed prior to final analysis, except that the whole database will be utilized.

We have chosen not to specify a planned interim analysis of the primary outcome, because we believe that interim analyses should be done only when there is an opportunity to end or change a trial while there is still time to make a difference (i.e., to prevent patients from being put onto or kept on an inferior treatment). The first time point at which an interim analysis could reasonably be completed would be near to the point in time when recruitment will have been completed. We would prefer not to obtain an interim analyses rather than lose statistical power by taking this additional look at the data. However, the specific report content and any interim analyses plans will be developed by the DCC statistician in collaboration with the DSMB.

### 23.3.2 Statistical Analyses

The Data Coordinating Center will form a Coordinating Center Data Analysis Committee which will include the Data Coordinating Center Director, Study Biostatistician, and Statistical Programmer.

The Data Coordinating Center statistician will work closely with the DSMB and clinical investigators to arrive at appropriate statistical analyses, consistent interpretation of the data, and clear and unequivocal presentation of the TRTT findings to the medical community. Statistical analysis responsibilities include:

- Defining the outcome(s) to be evaluated in conjunction with clinical study investigators;
- Describing the differences between the treatment groups being compared with respect to the baseline variables which might contain prognostic information, and with outcome(s) of interest;
- Evaluating the strength of the evidence regarding differences between the treatment groups and making decisions on the basis of the evidence; and
- Recommending one of the treatment strategies or concluding that no recommendation can be made.

Initial analyses will be descriptive in nature, using means, standard deviations, and proportions to describe baseline characteristics of the sample for all participants combined and by intervention group. Distributions of continuous variables will be examined for symmetry, and transformations will be considered for seriously skewed variables. For continuous variables, one-way analyses of variance will be used to compare the intervention groups on demographic and other baseline characteristics; the purpose is to assess comparability among the randomly assigned groups. For dichotomous or other categorical variables, chi-square tests will be used to compare intervention groups, and enrolled/excluded groups. Pearson correlation coefficients will be calculated to assess the strength of the associations among the various outcome measures, and to examine associations of other covariates with outcome measures; such potential confounding variables will be considered for inclusion in secondary analyses involving regression models.

All primary analyses will be based on the “intention to treat” principle. Analyses will include the following:

### 23.3.2.1 Primary Outcome

The primary outcome variable will be change in the TQ score. We will use spaghetti plots for initial exploratory analyses and longitudinal data analyses as our primary analytic method. Longitudinal analyses allows us to account for the natural correlation which occurs with observations on the same subject over time and for the same Audiologist observing several Study Participants. Indicator variables will identify group; their coefficients in the models represent the primary focus on group differences. Adjustment for covariates such as age and sex can easily be accounted for in this class of models.

Mean TQ scores will be compared between two treatment groups using Generalized Estimating Equations (GEE) as implemented in STATA, SAS or R. The basic model is as follows:

Let  $TQ$  denote the TQ score. We expect effects of Clinical Center, Audiologist, treatment group, and possibly personality traits as measured by the State-Trait Anxiety Index (STAI) or Positive and Negative Affect Schedule (PANAS); or other factors such as hearing difficulty measured using the Hearing Handicap Inventory (HHI), or early completion of treatment. We will use models of the form:

$$TQ_{ijkgt} = \beta_0 + \beta_c C_j + \beta_a A_k + \gamma_g G_g + \tau T_t + \rho_1 PT_{1i} + \rho_2 PT_{2i} + \varepsilon_{ijkgt}$$

where:

j indexes Clinical Center;  
k indexes Audiologist;  
g indexes Group;  
t indexes Time; and  
I indexes Study Participant.

Both Study Audiologist and Study Participant are nested within Clinical Centers. The parameter of interest is  $\gamma_g$ , with  $\gamma_1$  representing the difference between Group 1 (full TRT) and Group 3 (SC). (G represents a dummy variable for Groups).  $\beta_a$  and  $\beta_c$  provide comparisons between Study Audiologists and Clinical Centers; C and A are dummy variables.  $\tau$  captures the effect of time;  $T_1$  has the values of 0, 3, 6, 12, and 18.  $\rho_1$  and  $\rho_2$  capture differences in psychometric instruments measurements, e.g., the STAI and PANAS, respectively. Other factors may also be included as necessary ( $\rho_3$ ,  $\rho_4$ , etc.).

Similar models will be run for the secondary objectives. The mean TQ scores will be compared between the Group 1 (DC + conventional SG) and Group 2 (DC + placebo SG) for the superiority of the conventional SG; and between Group 2 (DC + placebo SG) and Group 3 (SC)

for the superiority of DC over the standard of care in reducing the severity of tinnitus among patients with severely debilitating tinnitus.

The GEE procedure has several useful features:

- It allows a flexible approach to modeling covariance structure, which results in a parsimonious covariance model.
- It uses the generalized least squares (GLS) method, which is generally superior to the ordinary least squares (OLS) method with an appropriate covariance structure.
- The presence of missing repeated measures for a subject does not result in exclusion of that subject from the analysis; instead, it uses all available data.
- It can be used to analyze different types of outcomes such as continuous, binary, or count.
- It can be used to analyze unbalanced design caused by either differing numbers of observations per person or by observations taken at different times.

We have included variables in the models to estimate the relationship between various personality characteristics and successful habituation to tinnitus in our basic model. Interaction terms between these patient characteristics and treatment group will be included to assess whether the effect of TRT is greater for certain types of patients. Personality characteristics of interest include those measured by the STAI and PANAS. Similar analyses will assess whether age, sex, or other patient characteristics are predictive of successful habituation with or without TRT.

In addition, the availability of information on the Study Participants will make it possible to learn about the impact of tinnitus in various demographic or other subgroups, and to assess whether the effect of TRT or TRT components varies between demographic subgroups and so we will perform valid analyses by gender, age, and minority status. We will also explore whether treatment with TRT or its components differentially impacts individuals with hyperacusis in conjunction with tinnitus versus those with only tinnitus, and whether and by how much initial tinnitus severity affects treatment efficacy.

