#### **Part 4: (to use if indicated)**

Elements of the initial TRT directive counseling may be reviewed, depending on the individual patient’s questions, concerns, and progress. Some of these concepts are:

- Auditory Gain
- The Heller Bergman Experiment
- The Neurophysiological Model of Tinnitus (*You could ask the Study Participant to explain the model to you to make sure s/he understands it.*)
- Conscious Loop
- Subconscious Loop
- Classification of New Sound as “Important” or “Unimportant”
  - Reclassification of Sound
  - Habituation of Reaction
  - Habituation of Perception
  - Reducing Contrast = Reducing strength
  - Sound Therapy
  - Habituation Takes Time

Examples used during Directive Counseling may be to help clarify these concepts for the Study Participant (*see Appendix B*).

**Part 5. Determining the end of treatment** (*See Section 11.4 for determining point at which to end treatment* )

Some Study Participants may feel that they have made sufficient progress in their treatment and that tinnitus and/or hyperacusis is no longer a significant issue in their life. There is no precise way to identify the end point or decide when a significant therapeutic effect has been achieved, but because this can occur sooner than the 18 months allotted by the TRTT, this must be considered.

The time to end treatment must be agreed upon between the Study Participant and the Study Audiologist. This point can occur after about one year of treatment or occasionally sooner. For the purposes of TRTT, if the Study Participant reaches the point where the tinnitus and/or hyperacusis is no longer an issue in his or her life, s/he may be instructed in how to reduce the use of the SGs and enriched environmental sound. Study Participants will, however, be required to continue to complete all TRTT Follow-up Visits and required ATH evaluations and psychometric measures.

The Study Participants's responses to the Follow-up TRT Interview provide a guide to whether tinnitus and/or hyperacusis is no longer clinically significant. In addition to change in the TRTT Follow-up Interview, Study Participants may report the following:

- The Study Participant may say, “Tinnitus is no longer an issue, what should I do?”
- The Study Participant may report they s/he has forgotten to wear the instruments for three or more weeks. This suggests that the Study Participant is forgetting about the tinnitus and is probably ready to stop wearing them.

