- The Study Participant may go for long periods of time when s/he is not aware of the tinnitus; even if s/he is aware of it, s/he is not bothered by it.
- Occasionally, individuals may be unable to hear the tinnitus, even with “hard listening”. (*This is not a goal of TRT, but happens to some people.*)
- The Study Participant reports that s/he is aware of tinnitus less than 10% of the time (*habituation of perception*).

- The Study Participant reports being annoyed/distressed/irritated by tinnitus as close to zero as possible over the past 1 to 2 months (*habituation of reaction*).
- The Study Participant reports that the “effect on life” of tinnitus and/or hyperacusis is as close to zero as possible.
- The Study Participant reports very few or no activities affected or prevented by tinnitus and/or hyperacusis over the past one to two months.
- The Study Participant reports very few or no bad days over the past one to two months and, if they occur, they are not as bad as they were originally.

**Review of standardized test results** at follow-up should indicate significant improvement compared to initial tests.

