### **Reducing Sound Therapy**

*(End of treatment, in this case, will mean reducing the use of SGs and enriched environmental sound. Study Participants will, however, be required to continue to complete all TRTT Follow-up Visits and required ATH evaluations and psychometric measures. This also allows the Study Audiologist to monitor the stability of the treatment effects.)*

To terminate treatment, it is important not to make rapid changes. In stopping the use of SGs, it is important to let the Study Participants know not to wear them intermittently, i.e., for several shorter periods each day (on/off) (*This draws attention to the symptoms*). Rather, they should stop wearing the devices certain days of the week (e.g., weekends) and then gradually stop the use of sound enrichment in the same way.

Finally, Study Participants can stop the use of enriched sound at night, although many individuals prefer to continue use of enriched sound at night as it helps them to sleep. They can continue to use the instruments periodically if considered necessary.

For Study Participants with tinnitus and hyperacusis, the hyperacusis is treated first with generally good results within the first 6 months. For some Study Participants with tinnitus and hyperacusis, when the hyperacusis is no longer an issue, the tinnitus is significantly improved.

If Study Participants reach this point before nine months of full TRT treatment, they should be required to wear the SGs and use enriched environmental sound for at least nine months.

---

---

## Chapter 12

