#### **14.6.6 Sound Generator Use Form**

The Sound Generator Use Form is completed by the Study Audiologist at T2, and at each follow-up visit. This form is used to record compliance of the individual with the recommended use of the sound generator; record change in volume setting, if required; and discontinuation of sound generator use at the end of treatment.

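### The primary model leaves room to adjust for early completion of treatment, a post-randomization event that the manual ties to response

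*Combined protocol and SAP*

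**What the plan says.** Section 23.3.2.1 introduces the primary GEE with a list of expected influences on the TQ: Clinical Center, Audiologist, treatment group, possibly personality traits, "or other factors such as hearing difficulty measured using the Hearing Handicap Inventory (HHI), or early completion of treatment". The equation contains center, audiologist, group, time and two participant-level psychometric terms, for which STAI and PANAS are the examples. After it the section adds: "Other factors may also be included as necessary". The parameter tested, γ₁, is the Group 1 minus Group 3 coefficient in this model.

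Section 23.3.2.1 does not define early completion. The follow-up counseling script (Chapter 11, Appendix D, Part 5) describes it:

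- The trigger is response. Sound use may be reduced "if the Study Participant reaches the point where the tinnitus and/or hyperacusis is no longer an issue in his or her life", and standardized tests "at follow-up should indicate significant improvement compared to initial tests".
- On timing: "This point can occur after about one year of treatment or occasionally sooner". The script also sets a minimum of nine months of sound therapy. The event therefore falls inside the 18-month outcome period.
- On meaning: "End of treatment, in this case, will mean reducing the use of SGs and enriched environmental sound".
- Section 14.6.6 has the Sound Generator Use Form record "discontinuation of sound generator use at the end of treatment".

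Sound generators go only to Groups 1 and 2 (Table 23.1). Chapter 13 describes counseling at T1 and T2 for standard of care and gives no rule for ending treatment. The SC follow-up form (Section 14.6.7) is completed at T2 and records compliance. Sections 23.3, 23.3.2 and 23.3.2.3 commit the analysis to intention to treat.

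**The concern.** A covariate that is a consequence of treatment, and close to the outcome itself, should not be in the model that estimates the treatment effect. If the flag is zero for everyone in SC, the flag's own coefficient absorbs the early completers. The group coefficient is then the mean of TRT participants who did not finish early minus the mean of all SC participants. One arm loses participants selected for doing well and the other loses none.

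The bias generally runs against TRT. If TRT works, the estimate moves toward no difference. If it does not, the estimate moves in favor of SC. The Group 2 versus Group 3 comparison has the same exposure.

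That the term is optional does not remove the problem. An analyst could choose, with data in hand, between versions of the primary model that estimate different quantities. Other parts of the plan are tighter: Section 23.3.2 sends potential confounders to secondary analyses, and Section 23.3.2.2 refers to baseline covariates for the 18-month ANCOVA.

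**Working it through.** **The plan's own figure.** Inputs from Section 23.2.3: 7-point difference, SD of change 12.5, two-sided α = 0.05/3 = 0.0167, power 80%, 10% attrition. The normal formula gives 67 per arm, or 75 after 67/0.9, total 225. A noncentral-t version gives 69, then 77 per arm, total 231. The stated 228 is reproduced and is not in question. With 76 × 0.9 ≈ 68 evaluable per arm, power for 10 points is 98.8%, consistent with the plan's claim of more than 95%.

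**Formula.** Let a share p of TRT participants be flagged, none in SC. Let r be the correlation between the variable driving the flag and the analysed outcome, and SD the outcome's standard deviation. Dropping the best share p from TRT reduces the estimated benefit by

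SD × r × k, where k = φ(z₁₋ₚ)/(1 − p).

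For p = 10%, k = 0.1755/0.9 = 0.195. For p = 20%, k = 0.2800/0.8 = 0.350.

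**Assumptions not in the documents.** p of 10% to 20%, in TRT only; equal correlation of 0.6 between visits; a constant 10-point effect; a flag set by 12-month TQ. A change SD of 12.5 then implies a single-visit SD of 12.5/√(2 × 0.4) = 13.98.

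**18-month difference, true value 10 points.**

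| Flag follows | Outcome analysed | r | p = 10% | p = 20% |
|---|---|---|---|---|
| 12-month level | raw score, SD 13.98 | 0.6 | 10 − 1.6 = 8.4 | 10 − 2.9 = 7.1 |
| 12-month change | change score, SD 12.5 | 0.5 | 10 − 1.2 = 8.8 | 10 − 2.2 = 7.8 |
| 12-month change | raw score | 0 | 10.0 | 10.0 |

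In the second row, r = (1 − 0.6)/(2 × (1 − 0.6)) = 0.5. In the third, the covariance of 12-month change with the 18-month score is proportional to 0.6 − 0.6 = 0, so nothing is lost.

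**Sensitivity.** For the first row at p = 20%, a visit correlation of 0.5 gives 10 − 12.5 × 0.5 × 0.350 = 7.8, and 0.7 gives 10 − 16.14 × 0.7 × 0.350 = 6.0. Treating r as free (0.3 to 0.8) with SD 12.5 and p from 10% to 30%, the 10 points become 9.3 down to 5.0.

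**Power and direction.** Simulation at one time point, 68 per arm, α = 0.0167, SD 12.5, r = 0.5: with a true 10 points, power is 94.5% (p = 10%) and 85.9% (p = 20%), against about 98.8% without the term. With no true effect, the adjusted estimate shifts 1.2 and 2.1 points in favor of SC, and significant results favoring SC occur in 3.4% and 7.3% of trials against a nominal 0.0167/2 = 0.8%.

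**Group 2 versus Group 3.** With r = 0.5 and SD 12.5, a true 7 points becomes 7 − 1.2 = 5.8 or 7 − 2.2 = 4.8.

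**The case against.** The strongest reply is that the plan never commits to this adjustment. The equation omits it, the added factors are discretionary, and the primary analyses are declared intention to treat. That stands, and it limits the point to an option that should be closed. It does not make the option harmless, because the section names this variable.

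Several stronger readings are tempting and are not supported:

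- *Early completion can occur only in the TRT arms.* This is inferred from what the text describes. No sentence excludes it for SC, and Section 11.4, to which the script refers, is not in the part of the manual available for this review. If SC participants could also finish early, the covariate would still be post-randomization and response-driven, but the size of the bias would differ.
- *Follow-up values of HHI, STAI and PANAS would also enter the model.* These scales are repeated at 6 and 18 months, but the psychometric terms carry a participant index and no time index. Section 14.5.5 collects only the state part of the STAI at follow-up, so its trait score exists only at baseline. Nothing proposes using the later values.
- *The bias is always toward no difference.* It runs against TRT, which under no true effect means away from zero.
- *The pooled five-visit coefficient would lose a known two to three points.* With a flag fixed by 12-month level and applied at every visit, it moves from −8.0 to −6.2 (10%) or −4.7 (20%). If the flag starts only at 12 months, in line with the nine-month minimum, the values are about −7.1 and −6.5. If the flag follows change and applies at every visit, nothing moves. The starting value of −8.0 instead of −10 arises because baseline is among the responses (10 × 4/5), a separate matter.

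The script also says that the end point cannot be identified precisely, requires agreement with the audiologist, and lets hyperacusis drive the decision. All three weaken the link to the TQ and argue for the smaller attenuations.

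**Conclusion.** The concern holds as a fault in an optional clause. Section 23.3.2.1 names a post-randomization, response-driven variable as a candidate influence in the primary analysis and sets no limit on what may be added. Using it would replace the randomized contrast with one that removes good responders mainly or only from TRT, against the plan's intention-to-treat commitment, and would generally bias the result against TRT.

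The size cannot be known from the documents. With 10% to 20% early completers in TRT only and a visit correlation of 0.6, a true 10-point difference at 18 months becomes about 7 to 9 points when the flag follows level and the raw score is analysed, or follows change and the change score is analysed. It can be unaffected when the flag follows change and the raw score is analysed. The conclusion that the term does not belong in the primary model depends on none of these figures.

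**What to change.** In Section 23.3.2.1:

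1. Delete early completion of treatment as a candidate covariate in the primary model.
2. Replace the open-ended sentence with a statement that, besides the group, time, Clinical Center and Audiologist terms already present, only covariates measured before randomization may enter, and list them.
3. If baseline TQ is added as a covariate, take T = 0 out of the responses so that the same measurement is not on both sides of the model.
4. Report early completion descriptively by arm, or in an analysis labelled exploratory.

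The cost is wording. No data collection, sample size or clinical rule changes.
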